8.3.3 Local laboratory values

Box plots of local laboratory values will be generated for baseline values and for values measured during the study by treatment arm and visit. Each box plot will show the first quartile, the median, and the third quartile. Outliers (values outside the box plot) will also be plotted. If appropriate, horizontal lines representing boundaries for abnormal values will be plotted.

For each local laboratory measure, summary statistics will be presented by treatment arm and timepoint, as well as changes from baseline for post enrollment values. In addition, the number (percentage) of participants with local laboratory values recorded as meeting Grade 1 AE criteria or above as specified in the Division of AIDS Table for Grading the Severity of Adult and Pediatric Adverse Events will be tabulated by treatment arm for each postvaccination timepoint. Reportable clinical laboratory abnormalities without an associated clinical diagnosis will also be included in the tabulation of AEs described above.

8.3.4 Reasons for vaccination discontinuation and early study termination

The number and percentage of participants who discontinue vaccination and who terminate the study early will be tabulated by reason and treatment arm.

8.4 Immunogenicity analysis

8.4.1 General Approach

For the statistical analysis of immunogenicity endpoints, data from enrolled participants will be used according to the initial randomization assignment regardless of how many injections they received. Additional analyses may be performed, limited to participants who received all scheduled injections per protocol. Assay results that are unreliable, from specimens collected outside of the visit window, or from HIV-infected participants post-infection are excluded.

Since the exact date of HIV infection is unknown, any assay data from blood draws 4 weeks prior to an infected participant's last seronegative sample and thereafter may be excluded. If an HIV-infected participant does not have a seronegative sample post enrollment, then all data from that participant may be excluded from the analysis.

Discrete categorical assay endpoints (eg, response rates) will be analyzed by tabulating the frequency of positive response for each assay by antigen and treatment arm at each timepoint for which an assessment is performed. Crude response rates will be presented with their corresponding 95% confidence interval estimates calculated using the score test method [1]. Because of the small numbers of control participants in each group, no adjustment will be made to the vaccine arm estimates for the false positive rates in the control arms. Barnard or Fisher's exact tests will be used to compare the response rates across treatment groups, with a significant difference declared if the 2-sided p-value is \leq 0.05; however the primary analysis will prioritize the one-sample comparison of those response rates to zero due to the power considerations

discussed above. In general Barnard's is preferred since under most circumstances it is more powerful than Fisher's [2].

In addition to response rate estimates for each timepoint, the probability of observing at least 1 positive response by a given timepoint and the probability of observing more than 1 positive response by a given timepoint will be estimated, with corresponding confidence intervals, for each vaccine arm using maximum likelihood-based methods [3].

For quantitative assay data (eg, magnitudes and magnitude-breadth AUCs from the neutralizing antibody multiplex assay), graphical and tabular summaries of the distributions by antigen, treatment arm, and timepoint will be made. For all primary and secondary immunogenicity endpoints, box plots and plots of estimated reverse cumulative distribution curves will be used for graphical display of all of the study arms. Typically, the results will be shown for each vaccine arm and for the set of control arms pooled into one group.

Some immunologic assays have underlying continuous or count-type readout that are dichotomized into responder/nonresponder categories (eg, nAb multiplex assay positivity). If treatment arm differences for these assays are best summarized by a mixture model, then Lachenbruch's test statistic [4] will be used to evaluate the composite null hypothesis of equal response rates in the 2 arms and equal response distributions among responders in the 2 such arms. This test statistic equals the square of a binomial Z-statistic for comparing the response rates plus the square of a Wilcoxon statistic for comparing the response distributions in the subgroup of responders. A permutation procedure is used to obtain a 2-sided p-value. For estimation, differences in response rates between arms will be estimated using the methods described above, and in the subgroup of positive responders, differences in location parameters between arms will be estimated using the methods described above.

Based upon previous HVTN trials as well as experience conducting infant clinical trials in the study population, missing up to 25% of immunogenicity results for a specific assay is anticipated due to study participants terminating from the study early, problems in shipping specimens, or low cell viability of processed peripheral blood mononuclear cells (PBMCs). To achieve unbiased statistical estimation and inferences with standard methods applied in a complete-case manner (only including participants with observed data in the analysis), missing data need to be missing completely at random (MCAR). Following the most commonly used definition, MCAR assumes that the probability of an observation being missing does not depend on any participant characteristics (observed or unobserved). When missing data are minimal (specifically if no more than 20% of participants are missing any values), then standard complete-case methods will be used, because violations of the MCAR assumption will have little impact on the estimates and hypothesis tests.

If a substantial amount of immunogenicity data is missing for an endpoint (at least 1 value missing from more than 20% of participants), then using the methods that require the MCAR assumption may give misleading results. In this situation, analyses of the immunogenicity endpoints at a specific timepoint will be performed using parametric generalized linear models fit by maximum likelihood. These methods provide unbiased estimation and inferences under the parametric modeling assumptions and the assumption that the missing data are missing at random (MAR). MAR assumes that the probability of an observation being missing may depend upon the observed responses and upon observed covariates, but not upon any unobserved factors. Generalized linear models for response rates will use a binomial error distribution and for quantitative endpoints, a normal error distribution. For assessing repeated immunogenicity measurement, linear mixed effects models will be used. If the immunological outcomes are left-and/or right- censored, then the linear mixed effects models of Hughes [5] will be used, because they accommodate the censoring. In addition, secondary analyses of repeated immunogenicity measurements may be done using weighted GEE [6] methods, which are valid under MAR. All

the models described above in this paragraph will include as covariates all available baseline predictors of the missing outcomes.

Some "resource-intensive" immunogenicity endpoints are only measured in subset of participants, eg, immunogenicity endpoints based on mucosal samples. For such endpoints, exploratory analyses will be conducted to assess the correlation of participant characteristics measured in (nearly) all participants with the resource-intensive endpoints. For example, if the same assay is performed on blood and mucosal samples, then a scatterplot and Spearman rank correlation coefficient (r) will be used to assess the correlation of responses. If at least moderate correlations exist (eg, $r \ge 0.3$), then the semiparametric efficient analysis method of Rotnitzky and Robins [7] will be used (described in Gilbert, Sato et al. for application to vaccine studies (83)) to estimate the mean of the resource-intensive endpoint for each group and to compare means between groups.

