Samples from two pediatric trials (PACTG 230 and PACTG 326) were then evaluated to determine immune responses in infants (see Table 4-9). In PACTG 230, infants were vaccinated between 0-20 weeks of age with four doses of Chiron rgp120 (SF2 strain) with MF59 (n=74), VaxGen rgp120 (MN strain) with aluminum hydroxide (alum, n=80), or adjuvant only placebo (MF59 or alum) (n=30) (65). In PACTG 326, infants received four doses of ALVAC-HIV alone (n=12), ALVAC-HIV with AIDSVAX B/B with the adjuvant alum (n=10) or placebo (n=12; n=8 saline & n=3 alum/saline) between 0-12 weeks of age (66). Infants developed robust Env-specific antibody responses to these first-generation HIV-1 Env vaccines. At one year of age, most maternally-acquired antibodies had waned, and vaccine Envelope-specific IgG responses were significantly higher in vaccinees compared to placebo recipients (21). Importantly, infants receiving the Chiron vaccine had higher and more durable IgG responses than adult vaccinees in the RV144 vaccine trial, with vaccine-elicited IgG responses still detectable in 56% of infants at two years of age. Remarkably, at peak immunogenicity, the concentration of anti-V1V2 IgG, a response associated with reduced risk of HIV acquisition in the RV144 adult vaccine trial, was 22-fold higher in infants who received the Chiron rgp120/MF59 vaccine/adjuvant combination than in RV144 vaccinees. V1V2-specific IgG3 responses, the subclass of the IgG response that best associated with protection in the RV144 study, were detected in 43% of the vaccinated infants at 24 weeks after vaccination. Finally, vaccine-elicited IgA responses rarely detected in the vaccinated infants. To determine if the difference in infant and RV144 adult responses was due to distinct vaccine regimens, the infant vaccine-elicited antibody responses were then compared to that of adults immunized with the same vaccine regimens (67). At peak immunogenicity, no difference was observed in the magnitude of gp120 or V1V2-specific IgG between adults and infants immunized with the Alum adjuvanted VaxGen vaccines; however, infants who received the MF59 adjuvanted Chiron vaccine had more robust responses than adults immunized with the same vaccine. Overall, these studies have multiple implications for the proposed clinical trial: 1) they demonstrated that infant vaccination can elicit high levels and durable Envspecific antibodies that have been associated with protection in vaccinated adults; 2) they indicate possible differences in how adjuvants modulate immune

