6.1.2 Sample size calculations for immunogenicity

To address binding antibody endpoints, the analysis will descriptively summarize binding response positivity call rates to test superiority of IgG binding Ab responses for CH103-like CD4bs and V1V2 for comparisons versus zero using binomial exact tests with 5% type-I error rate each. Note that if in HIV-infected women, maternal antibodies that differentially bind to the CD4bs occur at a rate of 51% [estimated from n = 14 CAPRISA 002 women infected 2-3 years (76) and are transmitted to the infants, comparisons at early timepoints may be confounded by background positivity. Therefore, we have chosen the 2 weeks post 5th vaccination timepoint (~ one year) for the power calculation. By this time, both transplacental and breastmilk-associated antibodies (breast-feeding typically ceases at 6 months of age in the South Africa setting) are expected to have waned to below detectable levels, obviating the requirement to increase the placebo recipient sample size for a comparison with this high background rate. The following calculations assume a 25% rate of missing data to accommodate missingness at the 1-year timepoint.

The main goals of this trial regarding immunogenicity outcomes involve a preliminary estimation of rates of "response" (defined for Primary Endpoint 2 as initiation of either the CD4bs or the V1V2 B cell lineage) based on data from immune assays among vaccinees. No adjustment for multiple comparisons will be

made for the use of multiple assays. The precision with which the true response rate can be estimated from the observed data depends on the true underlying response rate and the sample size. Two-sided 95% confidence intervals for the response rate based on observing a rate of responses in the vaccinees is shown in Table 6-3. Calculations are done using the score test method (75). The n=13 assumes a 25% rate of missing immunogenicity data.

Table 6-3 Two-sided 95% confidence intervals for the true response rate based on observing a particular rate of responses in the vaccinees (n = 13)

No. of responses	Observed response rate (%)	95% Confidence interval
1/13	7.7	[1.4, 33.3]
2/13	15.4	[4.3, 42.2]
3/13	23.1	[8.2, 50.3]
4/13	30.8	[12.7, 57.6]
5/13	38.5	[17.7, 64.5]
6/13	46.2	[23.2, 70.9]
7/13	53.8	[29.1, 76.8]
8/13	61.5	[35.5, 82.3]
9/13	69.2	[42.4, 87.3]
10/13	76.9	[49.7, 91.8]
11/13	84.6	[57.8, 95.7]
12/13	92.3	[66.7, 98.6]
13/13	100	[77.2, 100]

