6.4.4 Immunogenicity analysis

6.4.4.1 General approach

For the statistical analysis of immunogenicity endpoints, data from enrolled participants will be used according to the initial randomization assignment regardless of how many injections they received. Additional analyses may be performed, limited to participants who received all scheduled injections per protocol. Assay results that are unreliable, from specimens collected outside of the visit window, or from HIV-infected participants postinfection are excluded.

Since the exact date of HIV infection is unknown, any assay data from blood draws 4 weeks prior to an infected participant's last seronegative sample and thereafter may be excluded. If an HIV-infected participant does not have a seronegative sample postenrollment, then all data from that participant may be excluded from the analysis.

Discrete categorical assay endpoints (eg, response rates) will be analyzed by tabulating the frequency of positive response for each assay by antigen and treatment arm at each timepoint for which an assessment is performed. Crude response rates will be presented with their corresponding 95% confidence interval estimates calculated using the score test method (75). Because of the small numbers of control participants in each group, no adjustment will be made to the vaccine arm estimates for the false positive rates in the control arms. Barnard or Fisher's exact tests, as specified in the SAP, will be used to compare the response rates across treatment groups, with a significant difference declared if the 2-sided p-value is ≤ 0.05 ; however the primary analysis will prioritize the one-sample comparison of those response rates to zero due to the power considerations discussed above. In general Barnard's is preferred since under most circumstances it is more powerful than Fisher's (77).

In addition to response rate estimates for each timepoint, the probability of observing at least 1 positive response by a given timepoint and the probability of observing more than 1 positive response by a given timepoint will be estimated, with corresponding confidence intervals, for each vaccine arm using maximum likelihood-based methods (78).

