10.5 Endpoint assays: humoral

10.5.1 Binding antibody multiplex assay (BAMA)

HIV-1 Env binding IgG antibodies to the vaccine immunogens (EnvSeq-1 gp120 TF) will be assessed on serum/plasma samples from study participants taken at the primary immunogenicity timepoint and, due to the contributions of maternal antibody at birth, will be compared to matched samples from placebo controls. Conformational epitopes (eg, CD4BS specificities using differential binding to EnvSeq-1 gp120 TF compared to CH505 IΔ371 protein and sCD4 blocking) will be determined. Specimens from other timepoints as well as other HIV antigens (ie, other conformational epitopes and linear epitopes), IgA and antibody subclasses (IgG1, IgG2, IgG3, IgG4) may also be assayed based on the results of the initial assay. Cord blood, serum and/or breast milk samples may be tested to evaluate the effects of maternal antibodies.

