Both response magnitudes will be plotted and analyzed on a log scale. Both Definition 1 and Definition 2 are measured post-fifth vaccination. Definition 1 will be measured at baseline, while Definition 2 will also be measured at baseline for most IgG antigens except CH505TF.6R.SOSIP.664.v4.1_avi.2-Bio/293F, gp70_CH505TF_V1V2_avi/293F, and gp70_CH505TF_V1V2_N156KN160K_avi/293F. FcR data will be run at a single dilution (1:50) and therefore Definition 1 will be employed.

Primary antigens for analysis, with 'match' or 'mismatch' status with respect to the study vaccine, are as shown. Antigens considered 'wild type' vs. 'mutant type' are designated as such:

CH0505_CON D7gp120_avi/293/Mon	Matched	Wild type
CH0505_CON D7gp120_D368R_avi/293/Mon	Matched	Mutant type
CH505TF D7gp120d371_avi/293/Mon	Matched	Mutant type
CH505TFD8N156KN160K_avi/293i Mon	Matched	
CH505TF.6R.SOSIP.664.v4.1_avi.2-Bio/293F	Matched	
Con 6 gp120/B	Mismatched	
Con S gp140 CFI	Mismatched	
1086C_D7gp120.avi/293F	Mismatched	
gp41	Mismatched	
gp70_CH505TF_V1V2_avi/293F	Matched	
gp70_CH505TF_V1V2_N156KN160K_avi/293F	Mismatched	

Infant participant serum samples are assayed at visit 1 (cord blood), visit 2 (whole blood), and visit 12 (whole blood). For the analysis, visit 2 is considered as the preferred baseline, and when not available visit 1 will be used; we refer to this as 'v1/2'. Paired maternal serum samples at visits 2 and 12 are also assayed to assess maternal immune response.

As the study participants (infants) are HIV-exposed, the infant baseline responses are expected to be higher than usual due the influence of the maternal immune system. For this reason, visit 1/2 baseline values are not used in response calls. HVTN 115 Part A baseline data will be used as statistical baseline to determine the antigen specific positivity thresholds for HVTN 135, for the antigen(s) have the same detection and conjugate (dilution 1:50 and Isotype-Conjugate (ex. IgG-PE)) in the two studies.

Infant samples are declared to have a positive response if they meet the following three conditions:

- 1. net MFI values >= antigen specific cutoff values (max(95th percentile of statistical baseline, 100 net MFI))
- 2. net MFI values > 3x antigen specific median HVTN 115 baseline net MFI values
- 3. MFI values > 3x antigen specific median HVTN 115 baseline MFI values

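### The response-rate-versus-zero test is ranked first with a stated 5% type-I error, but it rejects on one positive infant and is within 5% only if the false-positive rate of the call is at most 0.39%

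*SAP*

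**What the plan says.** Protocol 6.1.2 plans to test the CD4bs and V1V2 IgG response rates "for comparisons versus zero using binomial exact tests with 5% type-I error rate each". Protocol 6.4.4.1 plans Barnard or Fisher tests between groups and continues: "however the primary analysis will prioritize the one-sample comparison of those response rates to zero due to the power considerations discussed above". SAP 8.4.1 repeats this ranking ("the primary analysis will prioritize the one-sample comparison of those response rates to zero") and adds that "no adjustment will be made to the vaccine arm estimates for the false positive rates in the control arms". Only the protocol attaches the 5% figure. The SAP cites power considerations discussed above, but it contains none.

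The power argument is in Protocol 6.1.2. With 13 evaluable vaccinees it claims more than 90% power at a true rate of 30%. Table 6-4, described as two-sided Fisher's exact at 0.05, shows low power for 13 vaccinees against 8 placebos.

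On background, Protocol 6.1.2 states that maternal antibodies "are expected to have waned to below detectable levels" by about one year. For BAMA positivity, SAP 9.3 states: "HVTN 115 Part A baseline data will be used as statistical baseline to determine the antigen specific positivity thresholds for HVTN 135". For B-cell phenotyping, SAP 9.5 sets the cutoff at the 85th percentile of the trial's own pooled placebo infants.

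**The concern.** Primary objective 2 asks whether vaccination initiates B-cell lineages. That is a causal question, and the trial has randomised placebo infants to answer it. The comparison ranked first ignores them and treats any positive call as evidence against zero.

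A null rate of exactly zero is credible only if the assay call never produces a false positive and no maternal antibody remains. The plan acknowledges that controls can have false positives and then declines to adjust for them. On maternal antibody, Protocol 4.8.3 is more cautious than 6.1.2: "At one year of age, most maternally-acquired antibodies had waned". The BAMA cutoff comes from HVTN 115 adults at baseline, so it cannot reflect residual maternal antibody in infants.

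A single false-positive call could therefore be reported as a significant vaccine response, with a 5% label suggesting that this risk is controlled.

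**Working it through.** **Inputs.** Groups 3 and 5 pooled: 18 enrolled, 25% missing assumed, 13 evaluable. Pooled placebo: 10 enrolled, 8 evaluable. Reference response rate in adults: 30% to 40%. All are from Protocol 6.1.1 and 6.1.2. No false-positive rate f is stated for any call, so every f below is an assumption.

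**Reproducing the plan's power figure.** An exact binomial test of p = 0 has p-value 1 at 0/13 and p-value 0 at 1/13, so it rejects at one or more positives. Power at 30% is 1 − 0.7^13 = 99.0%. The claim of more than 90% is correct, but it is only the probability of seeing at least one positive.

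**Size of the test.** Under a literal zero rate the size is 0. If an infant with no vaccine response is called positive with probability f, the size is 1 − (1 − f)^13. Setting this to 0.05 gives f = 1 − 0.95^(1/13) = 0.39%.

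| Assumed f | Size, n = 13 |
|---|---|
| 0.1% | 1.3% |
| 0.39% | 5% |
| 1% | 12% |
| 2% | 23% |
| 5% | 49% |

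**BAMA.** Criterion 1 in SAP 9.3 uses the larger of the 95th percentile of HVTN 115 baseline and 100 net MFI. On its own it would flag about 5% of such baseline samples whenever that percentile exceeds 100. Criteria 2 and 3 lower this to an unstated value, possibly zero. The six-criterion differential-binding call should be lower still.

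**B-cell call.** Null trials were simulated with 8 or 10 placebos, 13 vaccinees, no vaccine effect, and a responder defined as strictly above the placebo 85th percentile (200,000 trials per setting). SAP 9.5 does not say how the percentile is computed. For continuous untied data (normal, uniform, exponential, lognormal), the chance of at least one responder per subset and visit is about 82% to 88% under the R or SAS default and 69% to 77% under the (n+1)p rule. If only 1%, 5% or 10% of infants have non-zero values (assumed), it is 12%, 43% to 48%, and 59% to 71%. It reaches 5% only when about 0.4% of infants are non-zero.

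**Example.** With 1/13 vaccinees and 0/8 placebos the versus-zero test rejects, while Barnard gives p = 0.56 and Fisher p = 1.0. Against 0/8, Barnard needs at least 5/13 (p = 0.0497) and Fisher at least 6/13 (p = 0.0456). The score interval for 1/13 in Table 6-3, 1.4% to 33.3%, also excludes zero and could be misread in the same way.

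**Table 6-4.** Rejection regions for 8 versus 13 were fully enumerated. The table shows the vaccine response rate (%) needed for 80% / 90% power:

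| Placebo rate | Printed | Exact Fisher | Barnard |
|---|---|---|---|
| 0% | 64 / 73 | 53.9 / 59.8 | 46.3 / 52.3 |
| 10% | 79 / 87 | 73.6 / 80.4 | 68.7 / 76.8 |
| 20% | 89 / 95 | 83.4 / 89.5 | 80.1 / 86.3 |
| 30% | 96 / – | 90.2 / 94.4 | 87.2 / 92.3 |

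At the printed 64% and 73% with placebo at 0%, exact Fisher power is 95% and 99%. An arcsine approximation that moves each rate inward by 1/(2n) gives 63.5/72.9, 78.6/86.7, 88.4/94.9 and 95.4/none. Rounded up, these equal every printed entry.

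**Power of the placebo comparison.** At 30% and 40% response with no placebo responders, power is 17% and 43% by Fisher, and 35% and 65% by Barnard.

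**The case against.** The other side has real points.

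- **Inflation is not shown for BAMA.** The test is written out only for binding antibody, f is unknown there, and under a literal zero rate the size is 0. This stands. The sizes above 5% are conditional on assumed f.
- **SAP 9.5 names no test.** Versus-zero reaches the B-cell call only through the general rule in 8.4.1. This also stands, although that rule covers response rates for each assay.
- **Little depends on the test.** The primary endpoints are magnitudes and cell frequencies, Protocol 6.1.2 describes the goal as preliminary estimation, and rates are tabulated by arm. This limits the harm but does not make the 5% label correct.
- **Safeguards exist.** Protocol 10.5.1 says that BAMA samples, "due to the contributions of maternal antibody at birth, will be compared to matched samples from placebo controls", and SAP 9.3.2 adds exploratory gp41 and mother-infant plots. These help interpretation but do not set the size of the test ranked first.
- **A milder rule is available.** Requiring at least 2 of 13 responders keeps 93.6% power at 30%. It holds 5% only if f is at most 2.8%, which the plan does not establish.
- **Low power justifies the ranking.** The power concern is right in direction. It supports giving more weight to estimates with intervals, but not a test whose error rate is unknown.

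The past tense in parts of SAP 9.5 might suggest that B-cell data were already in hand. It does not show this, but the point should be confirmed before that analysis is changed.

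**Conclusion.** The concern holds, as a point that should be fixed. The stated 5% type-I error describes the versus-zero test only if f is at most 0.39% with 13 evaluable infants, and nothing in the documents supports such a bound. For BAMA, excess error is possible but unproven. For the B-cell call, if the general rule applies, at least one false responder is likely unless almost all values are tied at zero. Practical harm is limited because the aim is preliminary estimation and placebo comparisons are planned.

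The Table 6-4 mislabelling is secondary. Its entries are conservative, and the plan's conclusion of low power at 30% to 40% response survives correction.

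**What to change.** 1. **Protocol 6.1.2 and 6.4.4.1, SAP 8.4.1.** Drop the versus-zero test and its 5% label. Report vaccine-arm response rates with the planned score intervals as description, and state that a lower limit above zero is not by itself evidence of a vaccine response. Rest any claim that vaccination induced a response on pooled T3+T5 versus pooled placebo, using Barnard (already preferred) with a confidence interval for the difference.
2. **SAP 9.5.** Do not test the placebo-derived call against zero. Compare Env-specific and CD4bs-differential B-cell frequencies directly, T3+T5 versus pooled placebo, at visits 8 and 12, for example by Wilcoxon with an exact permutation p-value if values are tied. If the call is kept for display, state the percentile rule.
3. **Protocol 6.1.2.** Describe the figure of more than 90% as the probability of at least one responder. Replace Table 6-4 with exact Fisher or Barnard values, or name the approximation used.

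**Cost.** Text and analysis changes only, with no new infants, samples or assays. The formal comparison may be inconclusive, with 35% to 65% power by Barnard at the reference rates. The Wilcoxon comparison (8 versus 13, actual size 4.5%) has about 52% power at a shift of 1.0 SD and 80% at 1.4 SD, assuming a normal shift, and less with many ties.
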